STUDY PROTOCOL

Use of transcutaneous electrical nerve stimulation (TENS) for the recovery of oral function after orthognathic surgery

NCT ID not yet assigned

05/11/2020

ABSTRACT:

Oral functions of patients are markedly diminished immediately after orthognathic surgery, and novel approaches are needed to accelerate their recovery. The aim of this study will be to examine the usefulness of weekly applications of transcutaneous electrical nerve stimulation (TENS) for this purpose, based on evidence of its effectiveness in other types of patients with muscle alterations. Maximum jaw opening, bite force, pain, and facial inflammation will be compared between patients receiving TENS and those receiving sham-TENS for 30 min at baseline and weekly over a four-week period after orthognathic surgery and will be also compared between before and after each procedure.

MATERIAL

The sample will be made up of a sufficient number of patients according to the calculation of the sample size who will undergo bimaxillary surgery or mandibular surgery divided between experimental (TENS group) and control groups (sham-TENS).

Participants will be selected by non-probabilistic sampling of consecutive patients until the estimated sample size is reached. All patients have a skeletal and facial deformity amenable to surgery after a pre-surgical orthodontic period, and they will have to signed their informed consent after receiving an information sheet on the study.

This study was approved by the ethics committee of the hospital (San Carlos Hospital, Madrid, Spain).

Inclusion criterion:

- programing of bimaxillary or mandibular orthognathic surgery by the same surgeon in order to avoid inter-operator variability.
- no surgery for temporomandibular disorders or more complex syndromes,
- no presence of muscle or nervous disorders or receipt of medication for such disorders

Exclusion criterion:

- the impossibility to attend follow-up appointments
- the refusal of informed consent.

The sample size will be estimated to obtain a statistical power of 80% with an alpha error of 0.05 and 95% confidence interval to detect a difference in jaw opening ≥ 2.5 mm.

Patients will be randomly assigned to the experimental group for TENS application or the control group for sham-TENS and will be blinded to their group assignation, as was the researcher responsible for data analyses (single-blind randomized clinical trial).

METHOD

TENS procedure

An Enraf Nonius® S82 model TENS device will be used, with a maximum frequency of 220 Hz and an intensity range of 0 to 99.5 mA.

TENS electrodes will be placed bilaterally on mandibular elevator muscles, on the superficial masseter muscle above the gonial angle, and bilaterally on the anterior temporal muscle, following the manufacturer's instructions. The device will be applied in an identical manner to all patients in both groups and kept in position for the same time period (30 min); however, the device will be not switched on for the control group.

The stimulation intensity will be adjusted for those in the experimental group to the maximum that did not cause discomfort or areas of contraction, maintaining this stimulation intensity and frequency throughout the 30-min session.

Each participant will experience a weekly TENS or sham-TENS session on the same day of the week during a four-week period; appointments will be scheduled so as to minimize any possible interaction among study participants.

Study variables

Data will be gathered from all patients on jaw opening, bite force, inflammation, and pain before surgery and at 7, 14, 21, and 28 days post-surgery, conducting measurements both before and after the TENS/sham-TENS session.

Maximum Jaw Opening will be evaluated with patients seated vertically upright in the dental chair, using a digital dental caliber (Model R 100110, Mestra®) to measure the maximum opening from the incisal margin of upper central incisors to the incisal margin of lower incisors, adding the amount (in mm) of overbite or subtracting the amount (in mm) of open bite in occlusion.

Bite force will be measured using Dental Prescale Fuji® film, which is formed by microcapsules that generate a chemical reaction under pressure, staining the contact area with a color density corresponding to the pressure applied.

A sheet of the film will be placed between the occlusal surfaces of the two arches, and the patient will be asked to bite as strongly as possible for 5 sec. This procedure will be repeated three times, selecting the sheet with the best-defined tooth print to be photographed with a Canon® EOS 500 camera (RAW format, F32, and annular Flash) at the minimum distance permitted by the 75-macro lens.

The image will be processed in a Mac® computer to obtain the color value according to the Cie L*a*b* (CIELAB) scale, which gives the color a numerical value.

The corresponding pressure units (Megapascals, MPa) will be calculated according to Dental Prescale specifications, and the bite force (in Newtons [N]) will be obtained by using the following formula:

$$\text{Bite Force} = \text{Bite Pressure (MPa)} \times \text{mm}^2 \text{ print surface.}$$

Pain perceived by patients while autonomously opening and closing their jaws will be evaluated using a visual analog scale (VAS).

Facial inflammation will be measured (in mm) with patients seated upright in the dental chair, using a soft ruler to obtain a horizontal measurement from the lower border of the earlobe to the corner of the mouth and a vertical measurement from the gonial angle to the outer canthus of the eye. The soft ruler will be adapted to the contour of the patient's face without exerting any pressure.

All of the above measurements provided numeric values for treatment as continuous quantitative variables.

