### *Statistical analysis*

Descriptive statistics will be conducted to calculate distributions, frequencies, means and standard deviations for sex, malocclusion, and the results for maximum opening, bite force, inflammation, and pain in each group (experimental and control).

The Kolmogorov-Smirnov test will be applied to check the normality of variable distributions and Levene's test to check the equality of variances.

The Student's t-test will be employed to evaluate the difference in each measurement between experimental and control groups.

The paired Student's t-test will be used to compare measurements before and after TENS/sham-TENS in the same patient.

The GLM repeated-measures procedure will be applied to analyze the results for each group over time.

SPSS 22.0 ® for Windows will be used for statistical analysis

P≤0.05 was considered significant in all tests.

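### The plan does not say whether before-session or after-session readings support the recovery claim, and the immediate effect of a session is not compared with sham

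*Protocol*

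**What the plan says.** The Protocol abstract states the purpose: "Oral functions of patients are markedly diminished immediately after orthognathic surgery, and novel approaches are needed to accelerate their recovery". It announces a TENS-versus-sham comparison over the weeks after surgery, and adds that the outcomes "will be also compared between before and after each procedure".

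Under METHOD, TENS procedure, "Each participant will experience a weekly TENS or sham-TENS session on the same day of the week during a four-week period". The device is "kept in position for the same time period (30 min); however, the device will be not switched on for the control group". Under Study variables, data are collected "before surgery and at 7, 14, 21, and 28 days post-surgery, conducting measurements both before and after the TENS/sham-TENS session".

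In the SAP, Statistical analysis: "The Student's t-test will be employed to evaluate the difference in each measurement between experimental and control groups". The before/after question is given a paired t-test within patients, and results over time go to a repeated-measures GLM described for each group. One significance threshold serves all tests.

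The text available for review does not say which reading carries the recovery conclusion, which enters the GLM, or to which the 2.5 mm target under MATERIAL refers. A short part of the SAP was not available, so this silence is established only for the text seen.

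**The concern.** The two readings at a visit answer different questions. A before-session reading, taken about a week after the previous session, shows what the patient has kept. An after-session reading shows that plus anything the last 30 min produced, such as brief pain relief or muscle relaxation. Both are tested between arms by the same test at the same threshold, so an after-session difference may be offered as evidence of faster recovery when some or all of it is short-lived. Naming a single primary reading would not settle the matter if the one named were an after-session value.

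The immediate effect has the opposite problem. It is a legitimate objective, but its dedicated test looks at change within patients. Patients in the sham arm may also change over a session through rest, repeated opening or expectation, and a paired test does not remove that.

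**Working it through.** **What each comparison estimates.** Let L be the between-arm difference that has persisted to the start of a visit, T the between-arm difference added during the session, and S the change over a session in the sham arm.

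| Comparison | Estimates |
|---|---|
| Before-session reading, TENS minus sham | L |
| After-session reading, TENS minus sham | L + T |
| Paired before/after test, sham arm | S |
| Paired before/after test, TENS arm | S + T |
| After-minus-before change, TENS minus sham | T |

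Recovery is L. The SAP's t-test covers the first two rows without ranking them. Its paired test covers the third and fourth. The last row, which isolates the immediate effect against sham, is not specified. Whether any of T lasts can be seen only at the next before-session reading.

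**Which readings show L.** On the METHOD schedule, read as sessions on days 7, 14, 21 and 28, each outcome has 4 × 2 = 8 post-operative readings. Four are immediate. The day-7 before-session reading precedes any post-operative session. That leaves three before-session readings (days 14, 21 and 28) a week after an earlier session. Nothing follows the day-28 session except its immediate reading.

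**Size, as an illustration.** The plan gives no sample size or SD, so there is no figure to reproduce. From MATERIAL: 80% power, alpha 0.05, 2.5 mm. Assumed: two-sided test, 1:1 allocation, L = 0, and T either equal to the target or half of it.

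- Noncentrality at 2.5 mm: 1.96 + 0.84 = 2.80.
- T = 2.5 mm, one after-session test: Φ(2.80 − 1.96) = Φ(0.84) = 0.80.
- T = 1.25 mm: noncentrality 2.80 / 2 = 1.40; Φ(1.40 − 1.96) = Φ(−0.56) = 0.29.
- One before-session test with L = 0: false benefit 0.05 / 2 = 0.025.

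**Simulation check.** There were 5,000 trials per setting, with T = 2.5 mm and L = 0. SD was 3 or 5 mm (23 or 63 patients per arm), with equal correlation of 0.5, 0.7 or 0.9 among the eight readings; all of these are assumed. Two-sided rejection rates:

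| Test | Rate |
|---|---|
| One after-session reading | 0.785–0.798 |
| At least one of four after-session readings | 0.88–0.97 |
| Average of all eight readings | 0.30–0.46 |
| Day-28 before-session reading | 0.046–0.055 |
| At least one of three before-session readings | 0.08–0.13 |

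The third row shows why it matters which readings enter the GLM: averaging both kinds dilutes a transient effect but does not remove it. The last row shows why one before-session visit has to be named.

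**Precision of the change comparison.** With correlation ρ between the two readings at a visit, the SD of the change is SD × √(2(1 − ρ)). This is 1.00, 0.77 and 0.45 times the SD at ρ = 0.5, 0.7 and 0.9. Comparing changes between arms is therefore no less precise than comparing single readings once ρ is 0.5 or more.

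**The case against.** The strongest reply is that the plan already contains what is needed. The abstract announces the two comparisons separately, both readings are taken at every visit, and testing every measurement includes the before-session ones. A purely transient effect would be expected to show no difference there. This stands in large part. A reader might infer that the trial cannot tell transient from lasting benefit, or that a transient effect would be reported as recovery. The documents support neither: the separating data are planned, and selective reporting would be a guess. What remains is that nothing ties either kind of reading to the recovery conclusion, and that no stated test compares the immediate change with sham.

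A reader might also infer that a quarter of the course has its lasting effect unobserved, because the fourth session has no later reading. That relies on a session count the documents leave open. The abstract can be read as adding a session at baseline to the weekly ones, which would make day 28 the fifth. The protocol also promises nothing beyond day 28. Only a smaller statement holds under either reading: the session on day 28 has an immediate reading and no later one.

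Finally, the 80% figure is close to circular, since the transient effect was set equal to the difference the trial is powered for. That is correct, so it cannot be read as a forecast.

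**Conclusion.** The point holds as a gap between the aim and the stated analysis. As written, an immediate post-stimulation difference can count towards accelerated recovery, and the immediate effect itself is not tested against sham. This goes beyond a missing primary endpoint, because the choice between the two kinds of reading changes what is estimated (L or L + T).

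The illustrative size is about 80% significance at one after-session reading for a transient 2.5 mm and 29% for 1.25 mm, against 2.5% false benefit at a single before-session reading. These rest on an assumed effect with nothing lasting, a two-sided test and equal arms; they do not predict this trial's result. The day-28 session is a minor note that limits how a lasting benefit may be described. The plan should be amended before results are seen, since afterwards the choice of reading could follow the more favourable one.

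**What to change.** 1. Judge recovery on the between-arm difference in the before-session reading. Name one visit as the main test, for example day 28 before the session, and treat the before-session readings at the other visits that follow an earlier session as supporting.
2. State that the 2.5 mm target and the repeated-measures GLM apply to before-session readings.
3. Judge the immediate effect separately by comparing the after-minus-before change between arms. Within-arm paired tests may stay as description but should not carry the conclusion.
4. Word any statement on lasting benefit as referring to the sessions before day 28. Their number depends on reconciling the abstract with the METHOD schedule on whether there is a session at baseline.

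**Cost.** Only protocol and SAP wording changes: every reading is already planned, with no new visit and no change to treatment. The recovery claim becomes narrower and cannot draw on the likely larger after-session differences. At a given SD the sample size does not change if the full 2.5 mm is expected to persist. If only 1.25 mm persisted, power would be about 29%, and restoring 80% would need about four times as many patients (63 to 252 per arm at an assumed SD of 5 mm). The sponsor should therefore confirm that 2.5 mm is the difference intended for the before-session reading.

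### Bimaxillary and mandibular-only surgery are pooled with no stated stratification and an unadjusted between-arm test; adjusting for surgery type would be a cheap gain in precision

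*Protocol*

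**What the plan says.** The MATERIAL section of the protocol recruits two operations into one sample: patients "who will undergo bimaxillary surgery or mandibular surgery divided between experimental (TENS group) and control groups (sham-TENS". The inclusion criteria limit operative variation in one respect, requiring "programing of bimaxillary or mandibular orthognathic surgery by the same surgeon in order to avoid inter-operator variability". On allocation the protocol says "Patients will be randomly assigned to the experimental group for TENS application or the control group for sham-TENS". It gives no method, ratio, block size or stratification factor.

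The sample size is described only as "a sufficient number of patients according to the calculation of the sample size", with a "statistical power of 80% with an alpha error of 0.05 and 95% confidence interval" "to detect a difference in jaw opening ≥ 2.5 mm". No number of patients and no SD are given.

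In the SAP's Statistical analysis section, Student's t-test "will be employed to evaluate the difference in each measurement between experimental and control groups", and no covariate is named. A repeated-measures GLM is also planned, but only for each group's course over time; neither surgery type nor any other covariate is named for it. Sex and malocclusion are to be summarised by arm; surgery type is not on that list. Part of the SAP text was not available for review, so what is absent is judged on the text that can be seen.

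**The concern.** Surgery on one jaw and surgery on both are procedures of different extent. It is reasonable, though the documents do not say so, to expect them to differ in post-operative opening, bite force, swelling and pain. The protocol restricts to one surgeon because it regards operative variation as worth controlling, yet it leaves this visible operative difference unused. Surgery type is known before randomisation and needs no extra data.

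Two things follow if it matters for outcome. First, the spread between operations remains in the error term of the t-test, so the trial has less power than the same patients could give. Second, if by chance one arm receives more bimaxillary cases, the estimated TENS effect moves by that imbalance times the difference between operations. The planned comparison does not remove the shift, and the planned descriptive tables would not show the reader that it happened.

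**Working it through.** **Inputs from the documents.** Target difference 2.5 mm in jaw opening, power 80%, alpha 0.05 (MATERIAL). There is no sample size or SD to reproduce.

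**Assumed inputs.** Two-sided test, 1:1 allocation, no dropout, total SD 4 mm in the mixed population, half the patients bimaxillary (p = 0.5), and 42 per arm. At these values the unadjusted t-test has power 0.81. The share of variance due to surgery type, R², is varied over 4%, 10%, 20% and 30%.

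**Step 1: the gap implied by each R².** A difference of D mm between operations contributes variance p(1-p)D² = D²/4. Hence R² = D²/(4 × 16) and D = 8 × √R². R² of 10% gives D = 2.53 mm; 30% gives 4.38 mm.

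**Step 2: chance imbalance.** The SD of the difference between arms in the proportion bimaxillary is √(2p(1-p)/n) = √(0.5/42) = 0.109, about 11 percentage points.

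**Step 3: shift in the estimate.** 95% limit = 1.96 × 0.109 × D.

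**Step 4: power after adjustment.** The residual SD is 4 × √(1-R²), used in the two-sample t power calculation for 2.5 mm at 42 per arm.

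| R² | Gap D (mm) | 95% shift (mm) | Share of 2.5 mm | Residual SD (mm) | Adjusted power |
|---|---|---|---|---|---|
| 0 | 0 | 0 | 0% | 4.00 | 0.81 |
| 4% | 1.60 | 0.34 | 14% | 3.92 | 0.82 |
| 10% | 2.53 | 0.54 | 22% | 3.79 | 0.85 |
| 20% | 3.58 | 0.77 | 31% | 3.58 | 0.89 |
| 30% | 4.38 | 0.94 | 37% | 3.35 | 0.92 |

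**Step 5: dependence on the assumed SD.** If the trial is sized to its own target, the standard error of the difference is 2.5/(1.960 + 0.842) = 0.892 mm whatever the SD. The 95% shift is then 1.96 × R × 0.892 mm: 0.35 mm (14%) at R = 0.2, 0.52 mm (21%) at R = 0.3 and 0.87 mm (35%) at R = 0.5. So for a trial sized as the protocol intends, what matters is the share of variance explained, not the choice of 4 mm. Reaching about half the target (1.22 mm, 49%) needs R = 0.7, that is, surgery type explaining about half of all variance.

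**Step 6: validity of the unadjusted test.** Simulations with no TENS effect and unstratified allocation gave rejection rates of 0.049 to 0.050 (5 mm gap; SD 4, 5 and 6 mm; 41, 63 and 91 per arm; 20,000 trials each). Power was about 0.80 when the planning SD is that of the mixed population.

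**The case against.** The strongest reply is that nothing here is an error. Pooling two operations and comparing randomised arms without adjustment is a legitimate design. Chance imbalance is part of the sampling variation that the t-test's standard error already measures, and Step 6 bears this out. That stands in full. A reader might infer that the comparison is biased or confounded by surgery type; under randomisation it is not.

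A reader might also infer that allocation is by simple randomisation. The protocol says only that it is random, so a blocked or stratified list is not excluded. The supportable statement is that no stratification is stated.

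Nor do the documents show that imbalance could use up most of the 2.5 mm target. That reading needs a very small trial or a very large gap, and the figures then conflict with each other. At SD 4 mm and an even mix, an 8 mm gap contributes 8²/4 = 16 mm², which is the entire variance of 4² = 16. A 5 mm gap contributes 6.25 of 16, so surgery type would have to explain 39% of variance. With 20 per arm, a 5 mm gap would give a 95% shift of 1.55 mm (62% of target), but at SD 4 mm that trial has only 49% power, against the 80% the protocol requires.

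Finally, that the operations differ at all in these outcomes is clinical judgement, and with R² of 4% the gain is slight. That also stands, and is why the size is given as a range.

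What remains is practical. A 5% error rate over all possible allocations does not help to interpret one imbalanced trial. With 42 per arm, SD 4 mm, a 3 mm gap (R² = 2.25/16 = 14%) and a realised imbalance of 19 points, the unadjusted test rejects a true null about 8% of the time.

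**Conclusion.** The point holds as an inexpensive improvement in precision. It is not a bias and not a flaw in validity. In the text available, the plan pools two operations, states no stratification, uses an unadjusted between-arm test and does not provide for showing surgery type by arm.

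Under the stated assumptions, with surgery type explaining 10% to 30% of variance, the plan forgoes 4 to 11 percentage points of power (0.81 against 0.85-0.92). It also leaves a 95% chance shift of about 0.5 to 0.9 mm uncorrected. If surgery type explains little, the loss is about one point of power. Only the 2.5 mm target, the 80% power and the 0.05 level come from the protocol; the SD, sample size, mix and variance share are assumptions. No size can be given for bite force, swelling or pain, for which the documents state no target.

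**What to change.** In the SAP's Statistical analysis section, replace the unadjusted between-arm t-test with a linear model for each outcome that has arm and surgery type (bimaxillary or mandibular only) as prespecified fixed factors. This can be an ANCOVA, or the repeated-measures GLM already planned with arm as a between-subject factor. Report the adjusted difference between arms with its 95% confidence interval. Add surgery type to the variables summarised by arm.

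In MATERIAL, state the randomisation method. If enrolment has not started, use permuted blocks within the two surgery-type strata, and keep surgery type in the model, since stratifying without adjusting gives up the precision gained. If enrolment has started, leave allocation as it is and add only the covariate and the table row, specified before outcome data are examined by arm.

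The cost is one degree of freedom, a sentence in each document and, if stratified, two allocation lists instead of one. No additional data are needed.

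### The day-7 before-session reading appears to precede any TENS, yet the SAP gives it no baseline or covariate role when the arms are compared

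*Protocol*

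**What the plan says.** Under Study variables, the Protocol schedules the readings of all four outcomes (pain, facial inflammation, bite force and jaw opening) as follows: "before surgery and at 7, 14, 21, and 28 days post-surgery, conducting measurements both before and after the TENS/sham-TENS session". Under TENS procedure, "Each participant will experience a weekly TENS or sham-TENS session on the same day of the week during a four-week period". No sentence gives the day of the first session. The Abstract refers to patients "receiving TENS and those receiving sham-TENS for 30 min at baseline and weekly over a four-week period after orthognathic surgery" and does not define baseline.

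The SAP's Statistical analysis section says "The Student's t-test will be employed to evaluate the difference in each measurement between experimental and control groups", and then "The GLM repeated-measures procedure will be applied to analyze the results for each group over time". It applies a 0.05 threshold to every test. In the text available, no reading is named as baseline, covariate or exclusion, and no primary time point is given. The pre-surgery reading has no stated role either. Part of the SAP was not available, so these absences are judged only on the text supplied.

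On sample size, the Protocol aims for "statistical power of 80% with an alpha error of 0.05" to "detect a difference in jaw opening ≥ 2.5 mm", without saying at which visit, or before or after the session.

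**The concern.** A reading taken before a patient has received any stimulation cannot carry a treatment effect, so a difference between randomised arms at that reading is chance. If such a reading is tested alongside the others, a chance gap can be listed as a difference between TENS and sham. Because readings on the same patient are correlated, the gap also tends to persist at later visits, where it looks like sustained benefit or sustained harm.

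The same reading is also the most direct measure of how severe the deficit was just before treatment began. The pre-surgery value cannot show that, because it precedes the operation. To collect the reading and not adjust for it gives up precision that costs nothing.

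**Working it through.** **Which reading is untreated.** Weekly sessions over four weeks give four sessions. The post-surgical visits are days 7, 14, 21 and 28, also four, each with a before and an after reading (4 × 2 = 8). Matching the two lists places the first session on day 7. One of the eight readings, day 7 before the session, is then untreated and seven are treated. This is an inference. In the Abstract, the reference to baseline can attach to the sessions or to the comparisons. If it means a session before surgery, the only untreated reading is the one before that session, and the day-7 before-session reading is already a treated one.

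**Inputs.** From the Protocol: power 80%, alpha 0.05, difference 2.5 mm. Not given: sample size, SD and correlation between visits, so there is no stated figure to reproduce. Assumed: two-sided test, SD 4 mm (checked at 5 mm), a common correlation ρ of 0.3 to 0.9 between readings, and a constant effect after the first session.

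**Step 1, reference design.** n per arm = 2(1.96 + 0.84)² SD² / 2.5². At SD 4 mm this rounds up to 41. The SE is 4√(2/41) = 0.883, and 2.5/0.883 = 2.83, so power for one visit is Φ(2.83 − 1.96) = 80.8%. At SD 5 mm it is 63 per arm and 80.1%.

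**Step 2, chance of a gap at the untreated reading.** It is 5% for one variable. For at least one of four variables it is 1 − 0.95⁴ = 18.5%, and for five (counting the two facial measurements separately) 1 − 0.95⁵ = 22.6%, if independent. About half of these would favour TENS.

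**Step 3, carry-over.** With no true effect and a day-7 gap of 1.96 SE favouring TENS, the later z-statistic is normal with mean 1.96ρ and variance 1 − ρ². The chance that it exceeds 1.96 is 1 − Φ[(1.96 − 1.96ρ)/√(1 − ρ²)]. At ρ = 0.5 this is 1 − Φ(0.98/0.866) = 12.9%.

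**Step 4, adjustment.** Using the day-7 before-session reading as covariate changes the SD to SD√(1 − ρ²). At ρ = 0.5 power is Φ(2.83/0.866 − 1.96) = 90.4%.

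| ρ | Later visit significant for TENS after a 1.96 SE gap | One later visit, unadjusted | One later visit, adjusted |
|---|---|---|---|
| 0.3 | 7.5% | 80.8% | 84.3% |
| 0.5 | 12.9% | 80.8% | 90.4% |
| 0.7 | 20.5% | 80.8% | 97.7% |
| 0.9 | 32.6% | 80.8% | >99.9% |

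The unconditional value for the second column is 2.5%. After a gap of only 1 SE the figures are 4.1%, 4.6%, 3.9% and 0.8%, so carry-over matters mainly when the gap is large. At SD 5 mm with 63 per arm the adjusted powers are 83.7%, 90.0%, 97.6% and >99.9%.

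**Step 5, pooling, if it were done.** An equal-weight arm difference over the four before-session readings keeps (0 + 1 + 1 + 1)/4 = 75% of a constant effect. Over all eight post-surgical readings it keeps 7/8 = 87.5%. At ρ = 0.5 and SD 4 mm, power is 76.6% with day 7 included and 93.4% without it (four before-session readings), or 91.0% and 96.3% (all eight). A test at a single visit from day 14 on keeps 100%.

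**The case against.** The strongest reply is that the plan does nothing wrong as written. Randomisation keeps each single-visit test at its 5% level whether or not a baseline is used. An arm comparison before treatment can serve as a balance check. The term measurement may mean each variable and not each reading, because the Protocol closes Study variables by calling the outcomes measurements. The repeated-measures analysis is described for each group, which can be read as within-arm. The day of the first session is inferred, and part of the SAP was not available.

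Much of this stands. The error rate of each test, averaged over all possible gaps, is not inflated, so the harm is unadjusted chance imbalance, multiplicity and lost precision. But if measurement means variable, the SAP does not say which of the repeated readings is tested, and the untreated one still has no role. The precision argument depends on neither reading of that word.

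A reader might infer that the plan dilutes the treatment effect. The documents do not support that. Dilution needs the untreated reading to be pooled with later ones in a between-arm main effect, and the SAP states no such average. Separate t-tests at days 14, 21 and 28 are undiluted, and an arm-by-time contrast would use day 7 as its reference.

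**Conclusion.** The point holds in a limited form. On the most natural reading of the Methods, the day-7 before-session reading is untreated, and the available SAP text neither adjusts for it nor separates it from readings that can carry a TENS effect. The gain forgone is about 10 percentage points of power for one later visit at ρ = 0.5 (80.8% to 90.4%) and about 17 at ρ = 0.7 (to 97.7%). It is small at ρ = 0.3. These figures rest on an assumed SD, sample size and correlation; the gain depends mainly on the correlation and hardly on the SD.

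Two further inferences go too far. A reader might conclude that a day-7 difference will be presented as efficacy; no passage says so, only that nothing prevents it. A reader might also conclude that the Abstract contradicts the Methods; the wording is ambiguous and needs reconciling, but can be read consistently. This is worth correcting before analysis, and it does not invalidate the trial.

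**What to change.** 1. Reconcile the Abstract with the Methods on when the first session is given, and state its day.
2. Name the last reading before that session as the untreated baseline. If the first session proves to be earlier than day 7, the day-7 before-session reading is post-treatment and must not be used as a baseline covariate.
3. Compare the arms on later readings by ANCOVA, or by a repeated-measures model with arm and arm-by-time terms, using the baseline reading as covariate. Keeping it as the reference level of an arm-by-time contrast is also acceptable.
4. Report the baseline reading by arm descriptively, without an efficacy test. The paired before/after comparison within the session can still use it.

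The cost is Protocol and SAP wording only, with no new visits or data. The small downside is one fewer outcome occasion in the between-arm comparison.
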